## **Diabetes Attitude Scale (DAS)**

Items: 20

Scoring: Answers on a 5-point Likert scale from 1 (strongly disagree) to 5 (strongly agree) for all questions. 20 questions and 3 subscales were selected. Calculated mean score for each subscale.

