Items for each survey will be selected from previously validated measures and/or created by the PI. Items will be selected at the PI's discretion. All surveys and responses will be housed on Qualtrics. Participants will enter/create their unique personal ID before both survey sessions and before each education module. Participants may elect to complete the education training, but decline the option to participate in research.

If both the pre-assessment surveys and the post-assessment surveys are completed within 3 months, participants will be eligible to provide their information to be entered to win a \$40 Visa gift card. This identifiable information will only be collected to adhere to WashU institutional tax guidelines. This information will be collected using REDCap and will be stored separately from the research data.

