### **5.2.2 Secondary and Exploratory Outcome Variables (if applicable)**

- 1) Score change on Diabetes Knowledge test (overall and on subscores tied to content of each of 4 modules)
- 2) Score change on 3 subscales of the Diabetes Attitudes Scale-3
  - Patient Autonomy
  - Value of Tight Control
  - Importance of Specialized Training
- 3) Score change on Intention to Recommend Diabetes Prevention Measures Questionnaire (Newly Developed)
- 4) Percent of individuals accessing each module and pre-and post assessments
- 5) Validation of Self Efficacy for Providing Diabetes Education Scale
  - Correlation of baseline scale scores and General Self Efficacy Scale and Physician Teaching Motivation Questionnaire
- 6) Internal reliability statistics for all scales (Cronbach's alpha)

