#### **6.4.3.2 Secondary Objectives Analyses**

For GDM knowledge scores, we will compare scores before and after training for the overall diabetes knowledge test and for each of the subscales associated with the content of the 4 modules among the individuals that complete the training.

For Diabetes Attitudes scales, we will compare scores before and after training on each of 3 subscales (patient autonomy, value of tight control, importance of specialized training) among the individuals that complete the training.

For Intention to Recommend Diabetes Prevention Measures, we will compare scores before and after training among the individuals that complete the training.

To provide preliminary validation for the new self-efficacy scale, we will report correlations between the self-efficacy for providing diabetes education measure and the General Self Efficacy Scale and Patient Teaching Motivation Questionnaire. We will also report internal reliability statistics (Cronbach's alpha) for the self-efficacy for providing diabetes scale, Diabetes attitudes scale subscales, and Intention to Recommend Diabetes Prevention Measures.

We will report the number of individuals who complete the pretest, access each of the training modules, and complete the post test.

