### **Questions focused on value of tight control:**

In general I believe that...

9. There is not much use in trying to have good blood sugar control because the complications of diabetes will happen anyway.
10. Keeping the blood sugar close to normal can help to prevent the complications of diabetes.
11. Almost everyone with diabetes should do whatever it takes to keep their blood sugar close to normal.
12. Low blood sugar reactions make tight control too risky for most people.
13. People who have gestational diabetes will probably not get much payoff from tight control of their blood sugars.
14. Tight control is too much work.
15. Tight control of blood sugar makes sense only for people with type 1 diabetes.

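### The Diabetes Attitude Scale scoring rule gives no reverse-coding and no direction for the subscale score, although five of the seven value-of-tight-control items oppose tight control

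*Combined protocol and SAP*

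**What the plan says.** The DAS entry in the appendix has two scoring statements. The first sets the response scale: "Answers on a 5-point Likert scale from 1 (strongly disagree) to 5 (strongly agree) for all questions". The second sets the subscale score: "Calculated mean score for each subscale". Nothing there mentions recoding an item or says whether a higher subscale mean is the more favourable attitude.

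The seven value-of-tight-control items (9 to 15) are worded in both directions. Item 10 is in favour: "Keeping the blood sugar close to normal can help to prevent the complications of diabetes". Item 13 is against: "People who have gestational diabetes will probably not get much payoff from tight control of their blood sugars". So is item 14: "Tight control is too much work".

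Section 5.2.2 lists "Score change on 3 subscales of the Diabetes Attitudes Scale-3" as a secondary outcome. Section 6.4.3.2 says "we will compare scores before and after training on each of 3 subscales (patient autonomy, value of tight control, importance of specialized training", among those who complete training, and also plans Cronbach's alpha for the DAS subscales. Section 4.1 predicts improved attitudes toward the value of tight control, in words only. Section 6.1.3 refers to a survey code book, but only for reliability and validity statistics and references.

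**The concern.** A mean of agreement scores measures one attitude only if agreement points the same way on every item. Here it does not, and the items that point the other way are in the majority. An analyst who follows the written rule would get a score on which stronger support for tight control usually gives a lower number. Training that succeeded on this attitude could then be reported as having made it worse, or as having had little effect.

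Cronbach's alpha would be computed on the same unaligned items, so the subscale could look unreliable when the fault lies in the scoring. If the analyst instead reverses items on their own judgement, the choice of items is made outside the plan, possibly after the data have been seen.

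**Working it through.** **Item count.** The only checkable figure in the DAS scoring text is the number of items. The lists give 8 (autonomy, items 1-8) + 7 (tight control, items 9-15) + 5 (special training, items 16-20) = 20, which agrees with the text.

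**Item directions, from the wording.**
- Favour tight control: items 10 and 11 (2 items).
- Oppose tight control: items 9, 12, 13, 14 and 15 (5 items).
- All eight autonomy items and all five special-training items are worded in the direction of their construct, so those subscales need no reversal.

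**Score extremes.**
- Strongest supporter, as written: (2×5 + 5×1)/7 = 15/7 = 2.14.
- Strongest opponent, as written: (2×1 + 5×5)/7 = 27/7 = 3.86.
- With the five opposing items scored as 6 minus the response: 5.00 and 1.00.

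**Pre-post change.** Let dp be the mean improvement per item on items 10-11 and dn the mean improvement per item on items 9 and 12-15, both counted as positive toward tight control.
- As written: (2dp − 5dn)/7.
- Recoded: (2dp + 5dn)/7.

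A 1-point improvement on every item gives (2 − 5)/7 = −0.43 as written and +1.00 recoded. The product of the two numerators is 4dp² − 25dn², so the signs differ exactly when |dp| < 2.5|dn|. If attitudes improve overall (2dp + 5dn > 0), this reduces to dp < 2.5dn.

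The documents give no expected changes, so the values below are assumed.

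| dp | dn | As written | Recoded | Effect of the written rule |
|---|---|---|---|---|
| 0.5 | 0.5 | −0.21 | +0.50 | wrong sign |
| 0.4 | 0.2 | −0.03 | +0.26 | wrong sign |
| 0.5 | 0.2 | 0.00 | +0.29 | effect lost |
| 0.5 | 0.1 | +0.07 | +0.21 | attenuated |
| 0.3 | 0 | +0.09 | +0.09 | none |
| 1.0 | −0.2 | +0.43 | +0.14 | inflated |
| −0.5 | −0.5 | +0.21 | −0.50 | worsening shown as improvement |

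**Cronbach's alpha.** Let w be the common correlation within a direction and a the common correlation across directions after recoding. Seven items give 1 + 10 = 11 within-direction pairs and 2×5 = 10 across-direction pairs. Standardised alpha = (7/6)(1 − 7/S), with S = 7 + 22w + 20a recoded and S = 7 + 22w − 20a as written. The correlations are again assumed.

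| w | a | S as written | S recoded | Alpha as written | Alpha recoded |
|---|---|---|---|---|---|
| 0.3 | 0.3 | 7.6 | 19.6 | 0.09 | 0.75 |
| 0.4 | 0.3 | 9.8 | 21.8 | 0.33 | 0.79 |
| 0.4 | 0.1 | 13.8 | 17.8 | 0.57 | 0.71 |
| 0.4 | 0 | 15.8 | 15.8 | 0.65 | 0.65 |

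Alpha as written is the lower of the two only if a > 0.

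**The case against.** The strongest reply is that this is silence in a file that is not complete. The code book is not among the supplied pages, the outcome list names an established instrument, and Section 5.1 says "Items for each survey will be selected from previously validated measures and/or created by the PI". A reversal key may sit in either source. The reference to all questions can also be read as describing the response anchors only; the teaching-motivation questionnaire uses similar wording in that way. On that reading nobody intended to average unaligned items. This stands to the extent that the documents do not show an error in the analysis as carried out. It does not fill the gap. The scoring text goes from the anchors to the subscale mean with no recode between them, the code book is cited for other purposes, and the items are a selection made for this study.

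A second reply is that the planned alpha is a safeguard, since a value near 0.1 would prompt a check. That is fair when across-direction correlations are sizeable. It is weak at w = 0.4 and a = 0.1 (0.57 against 0.71), and absent at a = 0.

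A third is that higher meaning more favourable is the obvious inference from the subscale's name and the hypothesis. The favourable attitude is indeed clear. The written arithmetic does not deliver a score with that orientation.

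Finally, this is one secondary outcome in a pilot with no sample size calculation, and stored answers can be re-scored. That limits the severity of the point and also makes it cheap to settle.

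**Conclusion.** The concern holds. The written rule, applied exactly, ranks the strongest supporter of tight control below the strongest opponent. It gives the wrong sign for any overall improvement in which dp < 2.5dn, which includes an equal improvement on all items. For other patterns the change may be zero, attenuated, inflated or unaffected. The effect on alpha runs from none to a fall from 0.75 to 0.09 over the correlations tried.

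The 5-to-2 split and the score extremes follow from the item wording and the response scale alone. The sizes of the change and of alpha rest on assumed values, because the documents supply none.

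The reach is narrow: one of nine secondary pre-post comparisons (five knowledge scores, three DAS subscales, one intention score) and one reliability coefficient. The primary self-efficacy outcome is untouched. This should be fixed because the rule can reverse a conclusion on a listed outcome, but it does not threaten the main result.

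**What to change.** Add to the DAS scoring text:

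> Items 9, 12, 13, 14 and 15 are scored as 6 minus the response before averaging. A higher value-of-tight-control score means greater value placed on tight control. The pre-post change and Cronbach's alpha use the recoded items.

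If the code book already says this, cite it in the scoring text instead. The cost is this short addition and five recode lines in SPSS, the package named in Section 7.9. Section 7.8 says answers are held in Qualtrics by study ID, so the recode can be applied to data already collected without going back to participants.

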### **Questions focused on patient autonomy:**

In general I believe that...

1. The important decisions regarding daily diabetes care should be made by the person with diabetes.
2. Health care professionals should help patients make informed choices about their care plans.
3. People with diabetes should have the final say in setting their blood glucose goals.
4. The person with diabetes is the most important member of the diabetes care team.
5. People with diabetes should learn a lot about the disease so that they can be in charge of their own diabetes care.
6. What the patient does has more effect on the outcome of diabetes care than anything a health professional does.
7. People with diabetes have a right to decide how hard they will work to control their blood sugar.
8. People with diabetes have the right not to take good care of their diabetes.

### **Questions focused on value of tight control:**

In general I believe that...

9. There is not much use in trying to have good blood sugar control because the complications of diabetes will happen anyway.
10. Keeping the blood sugar close to normal can help to prevent the complications of diabetes.
11. Almost everyone with diabetes should do whatever it takes to keep their blood sugar close to normal.
12. Low blood sugar reactions make tight control too risky for most people.
13. People who have gestational diabetes will probably not get much payoff from tight control of their blood sugars.
14. Tight control is too much work.
15. Tight control of blood sugar makes sense only for people with type 1 diabetes.

### **Questions focused on need for special training:**

In general I believe that...

16. Health care professionals who treat people with diabetes should be trained to communicate well with their patients.
17. Health care professionals should be taught how daily diabetes care affects patients' lives.
18. It is important for the nurses and dietitians who teach people with diabetes to learn counseling skills.
19. Health care professionals should learn how to set goals with patients, not just tell them what to do.
20. To do a good job, diabetes educators should learn a lot about being teachers.

## **Gestational diabetes knowledge questions**

Items: 23

Score: Ratio total correct/total number.

Correct answers are highlighted.

23 questions total, subdivided by topic area:

Questions 1-5: Disease and complications knowledge

Questions 6-11: Weight, nutrition and physical activity knowledge

Questions 12-18: Medication and monitoring knowledge

Questions 19-23: Future risk and screening knowledge

1. Gestational diabetes occurs because:
  - 1) The body develops antibodies to the cells in the pancreas that make insulin (A)
  - 2) The placenta makes hormones that make the mother resistant to insulin
  - 3) The mother's pancreas can't make enough insulin
  - 4) B&C
  
2. Gestational diabetes is diagnosed in the US by:
  - 1) The HbA1C test
  - 2) A 3-hour 100 g oral glucose tolerance test with 2 or more abnormal values
  - 3) A 1 hour 50 g glucose challenge test
  - 4) Finger stick blood glucose testing
  - 5) A 2-hour 75g oral glucose tolerance test with 2 or more abnormal values
  
3. All of the following are possible complications from poorly controlled gestational diabetes except:
  - 1) Preterm labor
  - 2) Low blood sugar for infant at birth
  - 3) Placenta previa
  - 4) C section
  - 5) Large for gestational age infant
  
4. Which of the following are risk factors for gestational diabetes?
  - 1) Maternal age
  - 2) Hispanic ethnicity
  - 3) Maternal obesity
  - 4) All of the above
  
5. What is a good estimate of how common gestational diabetes is in the US?
  - 1) 2%
  - 2) 7%
  - 3) 15%
  - 4) 25%

6. If a woman starts pregnancy with a BMI over 30, how much weight should she gain if she is having one baby?

- 1) 28-40 lbs
- 2) 25-35 lbs
- 3) 15-25 lbs
- 4) 11-20 lbs

7. How many extra calories does a woman need during the 1st trimester?

- 1) None
- 2) 200
- 3) 400
- 4) 500

8. When choosing a vegetable, which of the following would have the least amount of carbohydrates?

- 1) Corn
- 2) Winter Squash
- 3) Spinach
- 4) Carrots
- 5) Peas

9. When choosing a fruit, which of the following would have the least amount of carbohydrates?

- 1) Blackberries
- 2) Grapes
- 3) Banana
- 4) Apple
- 5) Dried apricot

10. Which of the following meals would be the best choice for lunch for a woman with gestational diabetes?

- 1) Pizza and sweet tea
- 2) Ham and cheese sandwich with an apple
- 3) Baked potato with butter, sour cream, cheese, and bacon
- 4) Peanut butter and jelly sandwich with Sugar free pudding
- 5) Hard-boiled egg and string cheese

11. What exercise is considered safe during pregnancy?

- 1) Walking
- 2) Low impact aerobics
- 3) Weight lifting
- 4) Roller skating
- 5) A&B

12. What is the initial recommendation for blood sugar monitoring frequency during pregnancy with gestational diabetes?

- 1) Once a day at bedtime
- 2) Once a day in the morning
- 3) Fasting and 1 or 2 hours after each meal**
- 4) Twice a day before breakfast and dinner
- 5) Before each meal and at bedtime

13. If a woman with gestational diabetes requiring insulin has a normal blood sugar before a meal and is planning to eat a sandwich, she would need to take rapid acting insulin

- 1) True**
- 2) False

14. Which of the following medication(s) are not first line to treat gestational diabetes?

- 1) Metformin
- 2) Glyburide
- 3) Insulin
- 4) A and B**
- 5) A and C

15. Which times of day are her blood sugars too high?

- 1) Fasting in the morning
- 2) 1 hour post breakfast
- 3) 1 hour post dinner
- 4) A&C**
- 5) B&C

16. What insulin(s) are best to give as a rapid acting insulin with a meal that has carbohydrates?

- 1) NPH (Humulin R or Novolin N)
- 2) Regular (Humulin R or Novolin R)
- 3) Glargin (Lantus, Basaglar, or Toujeo)
- 4) Lispro (Humalog, Admelog)**
- 5) A and C

17. What symptoms might indicate that someone's blood sugar is low?

- 1) Sweating
- 2) Vomiting
- 3) Confusion
- 4) Abdominal pain
- 5) A&C**

18. If a woman's blood sugar is 59, what should she be told to do first?

- 1) Call the doctor
- 2) Drink a 20 oz soda and check blood sugar in an hour
- 3) Drink 4 oz of juice and check blood sugar in 15 minutes**
- 4) Eat a bowl of ice cream and check blood sugar before next meal

19. What percentage of women with gestational diabetes may go on to develop type 2 diabetes?

- 1) 10%
- 2) 30%
- 3) 50%**
- 4) 90%

20. Sam had gestational diabetes in her recent pregnancy and is now 2 weeks postpartum. What should she be told about getting screened for type 2 diabetes?

- 1) If they checked her blood sugar in the hospital and it was normal, she doesn't need further testing.
- 2) She should have a 2-hour oral glucose tolerance test at 4-12 weeks and a hemoglobin A1C every 1-3 years life long**
- 3) She should have a hemoglobin A1C now and every 1-3 years life long
- 4) She should have a 2-hour oral glucose tolerance test 4-12 weeks postpartum and if this is normal, she doesn't need further testing.

21. Anna's blood sugar was 152 mg/dl 2 hours after drinking 75g glucose at 6 weeks postpartum (this is consistent with impaired glucose tolerance or pre-diabetes). How often should she be screened for diabetes going forward?

- 1) Every 6 months
- 2) Every 1 year**
- 3) Every 3 years
- 4) Every 5 years

22. Metformin was as effective as lifestyle change at preventing diabetes among women who had gestational diabetes.

- 1) True**
- 2) False

23. Which of the following would not be helpful in making lifestyle change to prevent diabetes?

- 1) Increase non-starchy vegetable consumption
- 2) Stop drinking soda and drink juice instead**
- 3) Limit portion sizes
- 4) Increase moderate physical activity
- 5) Eat whole grains instead of refined grains

## Intentions for Diabetes Prevention

Items: 8

Scoring: Please rate the following statements on a scale of 1 (very unlikely) to 5 (very likely).

	Very unlikely	Somewhat unlikely	Neutral	Somewhat likely	Very likely
All questions	1	2	3	4	5

How likely are you to recommend that women with a history of gestational diabetes ...

1. Receive a diabetes screening test in the first 3 months after delivery
2. Receive a diabetes screening test at least every 3 years
3. Receive a diabetes screening test early (1st trimester) in the next pregnancy
4. Breastfeed, if able, for at least a little while after delivery
5. Breastfeed, if able, for more than 6 months after delivery
6. Continue the diet recommendations for gestational diabetes after pregnancy
7. Continue to get 150 minutes of moderate physical activity per week after pregnancy
8. Try to get back to their pre-pregnancy weight by one year postpartum
